### *Postoperative management*

Patients start early respiratory and physical therapy the day following surgery. An oral contrast study is performed on postoperative day 5–7 for total gastrectomy; after this study, the patient starts an oral diet and prophylactic drains are removed.

Esophagogastric junction (EGJ) cancer is classified according to Siewert classification[13]. In this study, only EGJ cancer Siewert types II and III are included. Patients are staged using *TNM Classification of Malignant Tumors*, seventh edition[14].

### *Complication assessment*

Severe 30-day or in-hospital morbidity is defined as a Clavien-Dindo score  $\geq 3$ [10]. The complication data is collected by each attending surgeon and together at a monthly conference. Complications detected upon readmission are also included in this study.

The complications are grouped into three categories: intraabdominal, wound–abdominal wall, and medical complication. We consider an esophagojejunostomy leak as the appearance of contrast outside the anastomosis, using an oral contrast study or CT scan, or by direct evaluation at reoperation. We consider a duodenal stump leak as the discharge of bile-containing liquid in drains or by direct evaluation at reoperation. A pancreatic fistula is considered as a drain output of any volume on or after postoperative day 3 with an amylase greater than three times the serum level.

### *Follow-up*

Standard follow up is at three-month intervals for two years, then at six-month intervals for three years, and yearly thereafter. Follow-up consists of physical examination, a complete blood count, liver-function testing, chest x-ray, abdominal ultrasound and CT-scanning, as clinically indicated. Patients are planned to have a minimum of 5 year follow-up.

### *Outcomes:*

The primary outcome of the study is severe 30-day or in-hospital morbidity.

The secondary outcome is long-term 5 year survival.

### *Sample size*

Using previously published data and given a 0.05 alpha level, a percentage of unexposed outcome of 10.8%, and OR 4.28, a sample size of 116 patients would yield at least 80% statistical power.

### *Statistical analysis*

Continuous variables are described by means and standard deviations or medians and interquartile range. Categorical variables are described with frequencies and percentage.

The following factors are analyzed: age, sex, comorbidity, American Society of Anesthesiologists (ASA) physical status, tobacco and alcohol consumption, body mass index (BMI), hematocrit, serum albumin level, tumor location, the use of preoperative chemotherapy, laparoscopic or open surgery, total or subtotal gastrectomy, duodenal stump closure, multi-organ resection, lymphadenectomy, reconstruction method, T status, lymph node metastasis, and resection margin. The T stage was grouped by T1–T2 and T3–T4 for analysis. Univariate and multivariate analyses are performed to identify predictors of severe postoperative morbidity; and predictors of long-term survival. All variables associated with severe morbidity with  $p < .05$  in the univariate analysis are subsequently entered into a Cox multivariate regression model with backward elimination. Significance is set at two-sided  $p < .05$ . All analyses are performed using the statistical SPSS IBM Statistics software program, version 22.

The local ethics committee approved this study. Informed consent of patients is waived because of the retrospective nature of the study. The study was designed in line with the PROCESS criteria[15].

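### The only written route into the multivariable Cox model is association with severe morbidity, so nodal status, margin or T status can be left out of the survival model

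*Combined protocol and SAP*

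**What the plan says.** All of this is in the combined protocol and SAP.

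- **Targets.** The Statistical analysis section has one list of candidate factors, ending in "T status, lymph node metastasis, and resection margin". It plans both univariate and multivariable work on "predictors of severe postoperative morbidity; and predictors of long-term survival".
- **Entry rule.** The same section then gives a single rule. "All variables associated with severe morbidity" at p < .05 in univariate analysis are "subsequently entered into a Cox multivariate regression model with backward elimination".
- **Outcomes.** The primary outcome is severe morbidity within 30 days or in hospital, which is binary. "The secondary outcome is long-term 5 year survival".
- **Aim.** The Introduction includes a comparison of long-term survival by complication status. Severe morbidity is not on the list of factors.

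No sentence links a univariate association with survival to entry into a multivariable survival model. No prognostic factor is kept in regardless of its p-value, and no logistic model is named.

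**The concern.** A covariate belongs in a survival model because it bears on survival. The written rule admits it because it bears on short-term complications. A factor that shortens survival without causing complications has only a chance-level route in, and backward elimination cannot bring it back because that step only removes terms.

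The Introduction names patient factors, local invasion, tumor location and several surgical factors as potential morbidity predictors. Nodal metastasis and margin are not among them. The rule therefore gives surgical factors a readier route in than two of the tumor factors on the list. The Operative procedure section ties multi-organ resection to direct tumor invasion, so at least one likely entrant is a marker of disease extent. With stage factors missing, such a variable can be reported as a survival predictor when it only stands in for stage. The comparison of survival by complication status is open to the same confounding.

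**Working it through.** **1. The plan's own figure.** The Sample size section is "given a 0.05 alpha level, a percentage of unexposed outcome of 10.8%, and OR 4.28", with 116 patients for at least 80% power.

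- Exposed rate: 4.28 × 0.108 / (0.892 + 4.28 × 0.108) = 0.462 / 1.354 = 34.1%.
- Two-sided comparison of two proportions, 1:1: n = [1.96√(2 × 0.2247 × 0.7753) + 0.8416√(0.0963 + 0.2248)]² / 0.2333² = 49.03, or 50 per group.
- Continuity correction: (49.03/4) × [1 + √(1 + 4/(49.03 × 0.2333))]² = 57.3, or 58 per group.

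The total of 116 is reproduced. It concerns the morbidity comparison only and says nothing about the survival model.

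**2. Chance that a factor passes the morbidity screen.** With d the difference in morbidity rates, and SE₀ and SE₁ the null and alternative standard errors, the chance is Φ((d − 1.96 SE₀)/SE₁) + Φ((−d − 1.96 SE₀)/SE₁). Morbidity in the unexposed is 10.8%. Prevalences and odds ratios (OR) are assumptions.

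| Patients | Prevalence | OR 1 | OR 1.5 | OR 2 | OR 3 |
|---|---|---|---|---|---|
| 116 | 50–60% (as for nodes) | 5% | 10–11% | 23–26% | 55–59% |
| 116 | 10% (as for margin) | 5% | 11% | 19% | 38% |
| 500 | 50–60% | 5% | 30–33% | 75–78% | over 99% |
| 500 | 10% | 5% | 19% | 45% | 83% |

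**3. Nodal status correlated with total gastrectomy, 116 patients.** From the plan: 10.8% and OR 4.28, applied here to total gastrectomy. Assumed: total gastrectomy in 50% with no effect on survival; nodal metastasis in 65% v 50%, or 70% v 45%, of total v subtotal gastrectomies.

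Worked case, 65% v 50%, no direct nodal effect on morbidity:

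- Share with total gastrectomy: node-positive 0.65/1.15 = 0.565; node-negative 0.35/0.85 = 0.412.
- Morbidity: node-positive 0.565 × 0.341 + 0.435 × 0.108 = 24.0%; node-negative 0.412 × 0.341 + 0.588 × 0.108 = 20.4%.
- With 66.7 and 49.3 patients expected, SE₀ = 0.0784 and SE₁ = 0.0776, so the chance of entry is Φ(−1.52) + Φ(−2.44) = 7%.

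With a direct nodal OR of 2, the four cell rates are 10.8%, 19.5%, 34.1% and 50.9%.

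| Nodal mix | Nodal morbidity OR | Morbidity, node-positive / node-negative | Entry by formula |
|---|---|---|---|
| 65% v 50% | 1 | 24.0% / 20.4% | 7% |
| 70% v 45% | 1 | 25.0% / 19.0% | 11% |
| 65% v 50% | 2 | 37.2% / 20.4% | 50% |
| 70% v 45% | 2 | 38.6% / 19.0% | 63% |

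**4. Effect on the survival model.** Simulated cohorts add a nodal survival hazard ratio (HR) of 2.5 and 65% five-year survival if node-negative. Each factor gets a chi-square screen on morbidity at p < .05. A Cox model is then fitted with whatever passed, without the backward-elimination step.

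| Nodal morbidity OR, two correlated mixes | Nodal entry, simulated | Total-gastrectomy HR (true 1.00) | False positives |
|---|---|---|---|
| 1 | 7–13% | 1.12–1.22 | 7–14% |
| 2 | 54–64% | 1.05–1.07 | near 5% |

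With nodal status always in the model, the HR is 1.00–1.01 and false positives are about 5%. Screened on survival instead, nodal status enters in 91–93% of samples. With nodal metastasis at 55% in both surgical groups there is no inflation (4.4%). Effects on survival of omitting resection margin were not simulated.

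**5. A stronger correlation.** Assume T3–T4 in 85% of node-positive and 40% of node-negative patients, nodal HR 3 and no true T effect. When nodes are omitted, T stage shows an HR of about 1.7 and is falsely significant in about 31% of runs at 116 patients, against 3–7% with nodes included.

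**The case against.** The strongest reply is that the entry sentence names only severe morbidity, so it may describe the morbidity model, with Cox written for logistic. That is plausible, and the survival rule would then be unstated, not wrong. It does not clear the plan: the sentence would name the wrong model for a binary outcome, and survival would have no entry rule.

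Three stronger readings may tempt a reader, and the documents do not support them.

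- *Nodal status and margin are usually left out.* Both are candidates. How often they fail depends on odds ratios, prevalences and cohort size that are not given. Nor is 116 the cohort size: Material and methods takes all consecutive patients. In a variant with T status as a candidate and a nodal morbidity OR of 2, nodes entered in 51–61% of samples at 116 patients and 90–98% at 300. A larger cohort is no safeguard without a direct nodal effect: false positives at 300 patients were then 10–22%.
- *Nothing is screened on survival.* Univariate survival analysis is planned. What is missing is the link from it to the multivariable model.
- *Stage is never in the model.* T status is listed, and the Introduction names local invasion as a potential morbidity factor, so T status can pass the screen.

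It is also fair that the harm is modest in the main illustration and falls on a secondary outcome.

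**Conclusion.** The concern holds in this form: the plan states no survival-based entry rule, and its one written rule, taken literally, selects survival covariates on a different outcome. That is unsound at any sample size, whichever reading of the sentence was intended.

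The size of the harm is not fixed by the documents. It runs from no inflation, when nodal status is unrelated to the retained factor, to a spurious HR of about 1.22 with up to 14% false positives in the 116-patient illustration. A retained factor more closely tied to nodal status could do worse. A moderate direct effect of nodal status on morbidity removes most of the problem. These figures rest on assumed prevalences, survival effects and correlations; only 10.8%, OR 4.28 and 116 come from the plan. The wording should be corrected before the survival analysis is run. This point does not alter the choice of covariates for the primary outcome.

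**What to change.** In the Statistical analysis section:

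1. Limit the severe-morbidity entry rule to a logistic model for severe morbidity.
2. Give the survival Cox model its own rule. Enter factors on their univariate association with survival, which is already planned, and keep T status, lymph node metastasis and resection margin in the model whatever their p-values. A survival-based rule alone would cure the main defect; keeping the three tumor factors guards against losing them to a screening p-value.
3. Make severe morbidity a term in the survival model, since the stated aim is to compare survival by complication status.

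The cost is a few sentences; all the variables are already collected. The downside is four fixed terms. In the assumed 116-patient scenario, five-year mortality is 35% if node-negative and 1 − 0.65^2.5 = 65.9% if node-positive. With 55% node-positive, expected deaths are 116 × (0.55 × 0.659 + 0.45 × 0.35) ≈ 60, or about 60/4 = 15 per fixed term. That is affordable, though it leaves limited room for further selected factors if the cohort is no larger than 116.

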## Introduction

Gastric cancer (GC) is the fifth most common cancer[1], with more than 900,000 new cases every year, and the third leading cause of cancer-related death worldwide[2].

Surgery and adjuvant treatment are the main treatment modalities for GC. Postoperative morbidity rates after gastrectomy vary across different studies, but total morbidity is more than 20–30% in most studies[3–8]. In a previous study by our group, morbidity was present in 31% of 1066 gastrectomies [9].

Data on postoperative morbidity predictors are heterogeneous. Patient (age, comorbidity, body mass index, serum albumin), tumor (local invasion and location), and surgery (open approach, total gastrectomy, lymph node dissection, and multi-organ resection) variables are described as potential factors for higher morbidity[3–5,8].

In our previous study, we did not have data on complication severity because this type of score did not exist at the beginning of that study[9]. In the past decade, complication severity has gained great importance, and use of the Clavien-Dindo classification has been widely adopted[10]. However, only a few studies have evaluated postoperative morbidity predictors according to complication severity for gastrectomy[6,7].

The aim of this study to identify predictors of severe postoperative morbidity after gastrectomy for gastric cancer (GC) and esophagogastric junction (EGJ) cancer and to evaluate long-term survival according to complications.

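### The only multivariable model named is Cox regression with candidates screened on severe morbidity, but that primary outcome is a yes/no event with no event-time or censoring rule

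*Combined protocol and SAP*

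**What the plan says.** The Introduction gives the first aim: "The aim of this study to identify predictors of severe postoperative morbidity after gastrectomy". Under Complication assessment, "Severe 30-day or in-hospital morbidity is defined as a Clavien-Dindo score" of 3 or more. The Outcomes section confirms the ranking: "The primary outcome of the study is severe 30-day or in-hospital morbidity", and "The secondary outcome is long-term 5 year survival".

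The Sample size section assumes "a percentage of unexposed outcome of 10.8%, and OR 4.28" and arrives at 116 patients for at least 80% power at an alpha of 0.05.

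The Statistical analysis section promises univariate and multivariate analyses "to identify predictors of severe postoperative morbidity; and predictors of long-term survival". The next sentence names the single multivariable model of the plan: variables with a univariate p below .05 for severe morbidity "in the univariate analysis are subsequently entered into a Cox multivariate regression model with backward elimination". Logistic regression, or any other model for a binary outcome, does not appear in the document.

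**The concern.** Cox regression needs a time origin, an event time and a censoring rule for each patient. The primary outcome has none of these. Its window also differs between patients (30 days, or longer for those still in hospital), and "Complications detected upon readmission are also included in this study", again without a dating rule. The sentence can be read in three ways:

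1. **Cox on the yes/no outcome with one common time for all patients.** With Breslow ties the coefficient is a log risk ratio, but the model-based standard error is too large.
2. **Cox on time to first severe complication.** This could be valid and would give a hazard ratio, but it needs onset and censoring rules that the plan does not state, in particular for in-hospital events after day 30.
3. **Cox meant only for 5-year survival.** The model suits that outcome. The primary outcome then has no stated multivariable model, and the survival candidates are chosen for their association with a different outcome.

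At stake is the study's main result. A reader cannot tell which effect measure will be reported or which test decides significance. In a retrospective study, a primary model left open can be settled after the data are seen.

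**Working it through.** **Inputs.** From Sample size: unexposed risk 0.108, OR 4.28, N = 116, alpha 0.05, power at least 80%. From Statistical analysis: two-sided testing. The split between exposed and unexposed is not given, so 58 v 58 and 23 v 93 are assumed below.

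**The plan's own figure.**
- Exposed odds = 4.28 × 0.108/0.892 = 0.518, so exposed risk = 0.518/1.518 = 0.341. The difference is d = 0.233 and the mean risk is 0.2247.
- Two proportions, 1:1: n = [1.96 √(2 × 0.2247 × 0.7753) + 0.842 √(0.108 × 0.892 + 0.341 × 0.659)]² / d² = 49.03 per group.
- With continuity correction: n′ = (n/4)[1 + √(1 + 4/(n d))]² = 57.3, rounded up to 58 per group, **116 in total**.

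The stated number reproduces exactly as a comparison of two proportions. The study was sized for a binary outcome.

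**One effect on three scales.**

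| Analysis | Measure | Value |
|---|---|---|
| Cox, common time, Breslow ties | risk ratio | 0.341/0.108 = 3.16 |
| Cox with onset times, event-free patients censored at day 30 | hazard ratio | about 3.64 |
| Logistic regression | odds ratio | 4.28 |

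The hazard ratio is the root of the limiting Cox score when both groups share the same onset pattern: 3.64 at 58 v 58, and 3.63 at 35 v 81 and at 23 v 93. Exact proportional hazards over a fixed window gives nearly the same: ln(0.659)/ln(0.892) = 3.65. Both leave out in-hospital events after day 30, because the plan does not say how to time them.

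**Standard error under reading 1 (one binary predictor).**
- 58 v 58: expected events are 58 × 0.341 = 19.8 and 58 × 0.108 = 6.26. Common-time Cox SE = √(1/19.8 + 1/6.26) = 0.458. Correct SE of the log risk ratio = √(0.659/19.8 + 0.892/6.26) = 0.419. The ratio is 1.09.
- 23 v 93: 0.476 v 0.416, ratio 1.15.

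**Power under reading 1.** Both binomials were enumerated exactly, with two-sided Wald tests at 0.05 and tables with a zero cell counted as non-significant.

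| Split | Common-time Cox | Logistic |
|---|---|---|
| 58 v 58 | 79.5% | 86.4% |
| 23 v 93 | 67.5% | 74.0% |

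A simulation of 3,000 data sets used two independent 58/58 predictors, one with OR 4.28 and one null. Power was 79.7% v 87.8%, and the type I error for the null predictor was 1.7% v 4.1% (Monte Carlo SE about 0.7 and 0.3 points).

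**Illustration on one data set, 20/58 v 6/58, common time.** Cox with Breslow ties returns 3.33, exactly the risk ratio, with SE 0.465. Efron ties return 3.83. Logistic regression returns an odds ratio of 4.56. Under this reading, even the choice of tie handling changes the reported figure.

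**The case against.** The sentence may be a drafting slip that merges a morbidity model and a survival model: the sentence before it covers both outcomes, and the sample size uses an odds ratio. Nothing shows that a common-time Cox fit is intended, and every standard-error and power figure above depends on that reading. On this view the proven fault is narrower: no usable multivariable model is clearly specified for the primary outcome.

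The power comparison is also sensitive to the test, and the plan does not say whether elimination uses Wald or likelihood-ratio tests. At 58 v 58, likelihood-ratio tests give 82.2% v 88.0%, so the gap of about 6 points remains but common-time Cox stays above 80%. At 23 v 93 logistic regression itself reaches only 74%, so most of that shortfall comes from the assumed split. Part of the conservatism is a Wald effect: at a common 10.8% event rate and 58 v 58, the Wald type I error is 2.1% for Cox and 3.0% for logistic regression, and the likelihood-ratio test brings Cox to 5.1%. At a common 22.5% rate Cox is conservative under both tests (2.3% and 2.9%).

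These limits on the figures stand, and the power figures should be taken as illustrative. The main point is untouched. A slip in the sentence that defines the primary model still has to be corrected, and the kindest reading, Cox for survival only, leaves the primary outcome without a model and the survival model with the wrong screening rule.

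**Conclusion.** The concern holds and must be fixed. It follows from the text alone: one multivariable model is named, its entry rule refers to severe morbidity, and that outcome is yes/no with no time structure. None of the three readings gives a complete and correct analysis of the primary outcome.

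The firm measure of its size is the scale ambiguity: the plan's own design effect would appear as 3.16, about 3.64 or 4.28. The loss of about 6 to 8 points of power applies only to reading 1, in the one- and two-predictor cases computed, under the assumed splits. No claim is made about error rates in the full screened model or under the other readings, and the severity does not depend on these figures.

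**What to change.** Name one model and one screening rule for each outcome, for example:

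> Severe morbidity (30-day or in-hospital) will be analysed by multivariable binary logistic regression, reporting odds ratios with 95% confidence intervals, with candidate variables screened on their association with morbidity. Cox regression will be used only for long-term survival, with candidate variables screened on their association with survival.

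Logistic regression is preferred because it matches the odds ratio used for sizing. A risk-ratio model with a correct standard error would also resolve the mismatch. So would a Cox model with stated onset and censoring rules, but that needs complication dates, which the plan does not mention collecting.

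The cost of the preferred change is two sentences. It needs no new data, and 116 stays as it is because it already comes from a binary-outcome calculation. The screening threshold and backward elimination are outside this point and are left as they are.
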